Effect of Presenting Survival Information as Text or Pictograph During Periviable Birth Counseling

NCT04859114

May 10, 2022

Study Protocol

- Background
 - In the event of perivable birth, or delivery between 22-24 weeks gestational age (GA), professional guidelines (e.g., from the American College of Obstetricians and Gynecologists) recommend parents participate in decision making for either intensive care or palliative care for the baby.
 - It has been assumed by clinicians that the baby's chance of survival would influence parents' treatment choice. In a 2020 study published in JAMA Pediatrics, Kidzun et al. randomized women to see either a 30% or 60% chance of survival, and they found the chance of survival did not affect their hypothetical perivable birth treatment choice.
 - However, Kidzun et al. did not assess participants' comprehension of the chance of survival and could therefore not address the possibility that participants simply did not understand the chance of survival.
 - Their study also provided the survival information as only text information. Health risk communication recommendations specific that pictographs (also known as icon arrays) are a preferred method for communicating such information.
 - Finally, the Kidzun et al. study did not address the role of intuitive beliefs in decision making. Intuitive beliefs (i.e., intuition or gut feelings) have been reported by families as influential in medical decisions.
- Aims
 - We sought to determine if presenting a physician's estimate of a 30% or 60% chance of survival would affect treatment choice and if the format in which those probabilities are presented would affect treatment choice.
 - We were also interested in what participants would recall about the physician-provided estimate of survival and how their intuitive beliefs about their baby's chance of survival may be different from that estimate.
 - We aimed to explore if recall of physician's estimate or intuitive beliefs were better predictors of treatment choice.
- Methods
 - Design
 - Factorial experiment
 - Between-subjects
 - Participants randomized (1:1) to 1 of 6 groups:
 - | Probability Communication Format | Physician's estimate of survival | |
|----------------------------------|----------------------------------|-----|
| | 30% | 60% |
| Text-Only | 1 | 2 |
| Static Pictograph | 3 | 4 |
| Iterative Pictograph | 5 | 6 |

 - Hypothetical case scenario delivered through the internet survey tool Qualtrics
 - Participants
 - Recruited online via internet-based recruitment company Dynata
 - Received points redeemable for gift cards or charitable donations
 - Women in the U.S. of child-bearing age (18-50 years old)

- Vignette
 - Case was adapted from Haward et al. (2008)
 - Gave participants:
 - General prematurity information
 - Information on birth at 22 weeks GA
 - Description of intensive care and palliative care
 - Adapted from Kidszun et al (2020)- randomized participants to 30% or 60% chance of survival
 - Written information
 - Out of 10 babies born in this situation and given intensive care, [3 or 6] would survive, and of those, [1 or 2] would survive without a disability.
- Probability communication format
 - Next page repeats the chance of survival and disability for all groups.
 - Randomized to the chance of survival and disability as:
 - Text only: Repeat of the text information seen before
 - Static pictograph: A set of 10 baby icons, each colored differently depending on their outcome.
 - Iterative pictograph: A sequence of 10 pictograph images. Each image is similar to the static pictograph, the outcomes were randomly shuffled and an icon bordered in orange represented the participant's baby. The goal was to allow participants to experience the outcomes if 10 such decisions were made for intensive care in this situation.
- Outcome measures
 - Treatment choice
 - Asked to choose if they would want intensive care or palliative care for their baby in this situation.
 - Recall of physician estimate
 - "Based on the information the doctor showed you earlier, for every 10 babies born at 22 weeks and given intensive care, how many would survive?"
 - Answered on a scale from 0-10.
 - Based on their response for the chance of survival, they were asked a follow up question about how many of those that survive would go on to show a disability.
 - Intuitive beliefs
 - Adapted from Windschitl (2003)
 - "Assume again that your baby was born prematurely at 22 weeks and given intensive care treatment. The doctor gave you the same information you read earlier. At a gut level, what would you believe is *your own baby's* actual chance of survival?"
 - Answered on a sliding scale from "No chance of survival" to "Definitely will survive"
 - Automatically converted to a 0-100 scale in Qualtrics
 - Participant characteristics collected:

- Preference for medical autonomy vs. medical paternalism
 - Adapted from Haward et al. (2008)
- Prioritization of sanctity vs. quality of life
 - Adapted from Haward et al. (2008)
- Health literacy
 - Brief Literacy Screen
- Numeracy
 - Subjective Numeracy Scale (SNS-3)
- Religiosity
 - Duke University Religion Index (DUREL)
 - 3 subscales:
 - Organizational religiosity (e.g., service attendance)
 - Nonorganizational religiosity (e.g., prayer)
 - Intrinsic religiosity (i.e., subjective religiosity)
- Number of children
- Previous exposure as a parent to the NICU
- Race
- Ethnicity
- Education
- Year of birth
- Statistical analysis:
 - Power analysis
 - Estimated 60% of participants choosing intensive care
 - Detecting a 15% difference between study groups with at least 80% power and alpha of 0.05
 - Sample size of 1,050 necessary
 - Comparing 2 groups:
 - Fisher's exact test to compare categorical variables
 - Mann-Whitney test to compare continuous variables
 - Comparing >2 groups:
 - Fisher's Freeman-Halton to compare categorical variables
 - Kruskal-Wallis to compare continuous variables
 - Classification and regression tree analysis (CART)
 - Nonparametric, multivariable modeling approach to identify interrelationships and possible thresholds
 - Assessed the explanatory power of experimental variables and participant characteristics on treatment choice (binary outcome)
 - Optimized by Gini method
 - 10-fold cross validation
 - Split criteria of 10 for the parent node and 5 for the terminal nodes

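### Must the plan say how the iterative pictograph was shuffled, and whether the participant's own baby survived in exactly 3 or 6 of the 10 images?

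*Combined protocol and SAP*

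**What the plan says.** The Design item gives a between-subjects factorial: "Participants randomized (1:1) to 1 of 6 groups", with three formats crossed with a 30% or 60% survival estimate. Groups 5 and 6 receive the iterative format.

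Under Vignette, every woman first reads the assigned figures in words: 3 or 6 survivors out of 10, of whom 1 or 2 have no disability. Under Probability communication format, "Next page repeats the chance of survival and disability for all groups". For groups 5 and 6 that page is described as follows: "Iterative pictograph: A sequence of 10 pictograph images". Each image resembles the static pictograph, and "the outcomes were randomly shuffled and an icon bordered in orange represented the participant's baby". The purpose is given: "The goal was to allow participants to experience the outcomes if 10 such decisions were made for intensive care in this situation".

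The Aims ask whether the survival estimate and the format affect treatment choice. Separately, they ask what women recall of the estimate and "how their intuitive beliefs about their baby's chance of survival may be different from that estimate". The Statistical analysis section lists group comparisons and a classification tree. No analysis uses the number of survivals a woman saw for the marked baby.

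**The concern.** The description leaves two questions open. Was the shuffle drawn for each woman, or was one set shown to everyone in a group? And was the marked baby's total over the 10 images held at the assigned number or left to chance? The answers combine freely, since a fixed set may or may not be constrained. Resemblance to the static pictograph settles only the mix of outcomes within an image. The stated goal fits either a free or a held total.

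The point seems to matter because the marked baby is described only for this format, while the intuitive-belief item asks about the woman's own baby. If totals varied, two women given the same estimate could have watched quite different runs of luck. If one unconstrained set was shown to a whole group, the effect of the format could not be told apart from the effect of that particular run. In either case a reader could not rebuild the stimulus from the text, and an effect of the iterative format on belief would be harder to interpret.

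**Working it through.** **Inputs from the protocol.** Total 1,050 and six equal groups (Power analysis; Design); 10 images; assigned survival 3 or 6 of 10; assigned disability-free survival 1 or 2 of 10, taken to pair with 3 and 6 in that order. Planned group size: 1,050 / 6 = 175.

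**1. The plan's own figure.** The Power analysis item states "Estimated 60% of participants choosing intensive care", a 15% difference (taken as absolute), at least 80% power and alpha 0.05 (taken as two-sided). For 0.60 against 0.45, the mean proportion is 0.525, and

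n = [1.960 × √(2 × 0.525 × 0.475) + 0.842 × √(0.60 × 0.40 + 0.45 × 0.55)]² / 0.15² = 172.8, so 173 per group.

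6 × 173 = 1,038, about 1% below 1,050. The calculation uses only the proportions choosing intensive care in each group. The marked baby's total does not enter it.

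**2. Do the planned tests depend on the mechanism?** Let k be the marked baby's survivals over the 10 images. If k varies by woman, the chance that a woman in a given group chooses intensive care is Σ P(k) × P(choice given k). Women draw k independently of one another, so each choice is still an independent yes/no outcome with that single group probability. There is no extra variance, and the exact and rank tests keep their size. If k is fixed within a group, the sum has one term and the same conclusion holds. Because the shuffle follows allocation, it is part of the treatment and cannot bias the comparison of groups as delivered.

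**3. How far could totals stray?** Assume independent shuffles for each woman, so that k is Binomial(10, p).

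| | 30% group | 60% group |
|---|---|---|
| Mean = 10p | 3 | 6 |
| SD = √(10p(1 − p)) | 1.45 | 1.55 |
| P(exactly the assigned total) | 0.267 | 0.251 |
| P(any other total) | 0.733 (about 128 of 175) | 0.749 (about 131 of 175) |
| P(within one of it) | 0.700 | 0.666 |
| P(marked baby never survives disability-free) | 0.9¹⁰ = 0.349 (about 61 of 175) | 0.8¹⁰ = 0.107 (about 19 of 175) |

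For a random pair, one woman from each group, the 30% woman sees fewer survivals with probability 0.880, the same number with probability 0.068, and more with probability 0.052. The average contrast stays at 6 − 3 = 3 survivals.

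**4. The other readings.** If the total is constrained, every woman sees the assigned number and the spread is zero. If one set per group was drawn at random without constraint, each group's total is a single constant. The chance that at least one of the two constants misses its assigned figure is 1 − 0.267 × 0.251 = 0.933.

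**The case for a change.** The strongest case for acting is the fixed, unconstrained set. By step 4, at least one iterative group would then very probably have seen a marked-baby total other than its assigned one, and in that group format and total could not be separated. This format takes a planned third of the sample, and the authors could settle the question in a sentence or two. If totals varied and were stored, relating them to belief in groups 5 and 6 would use data already collected. With 350 women, 80% power is reached at a partial correlation of about tanh((1.960 + 0.842) / √346) = 0.15.

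Part of this stands. The mechanism is not in the text, and a report of the study would be clearer with it. Where totals were constant within a group, giving them would help a reader interpret the format result.

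The rest does not carry weight against the plan. Nothing shows that an unconstrained fixed set was used. Every woman also read the assigned figures in words beforehand. If each image keeps the static pictograph's mix, as its described resemblance suggests, she saw the assigned proportion 10 times over, so the marked baby's run is one added cue. The belief item itself refers back to the doctor's information. The aim on intuitive beliefs compares belief with the physician's estimate and does not mention format; format is tied to treatment choice. Chance variation over 10 draws is also consistent with the display's stated purpose. The correlation analysis is not one the plan proposes. It would be impossible without stored totals and uninformative if totals were constant, and it would correct no planned result.

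**Conclusion.** No change to the plan follows. The protocol is a short outline, and this is a missing detail of the display that those who built it can supply when they describe it. Every planned comparison keeps its validity, and 1,050 stands, whether the shuffle was per woman or fixed, free or constrained.

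The share of women seeing a total other than the assigned one runs from 0% under a constrained total to 73% and 75% under independent per-woman shuffles, and is either 0% or 100% in each group under a fixed set. The 73% and 75% rest on an independence assumption that the documents neither state nor exclude, and they count a miss by one as a miss. They describe what free shuffling would produce and should not be read as the size of a flaw. What remains is a limit on interpretation: a result for the iterative format applies to the display as built, and its reading in terms of the marked baby depends on how that display was generated.

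### Treatment choice is compared by unadjusted tests with no effect estimate, interval or interaction contrast, and the collected characteristics enter only the CART

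*Combined protocol and SAP*

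**What the plan says.** The document is the Combined protocol and SAP. Under Methods, Design, it describes a between-subjects factorial experiment: "Participants randomized (1:1) to 1 of 6 groups", crossing two survival estimates (30%, 60%) with three formats.

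Under Statistical analysis, two-group comparisons use "Fisher's exact test to compare categorical variables" and "Mann-Whitney test to compare continuous variables". For more than two groups the tests are Freeman-Halton and Kruskal-Wallis. No risk difference, odds ratio, confidence interval, margin, adjusted comparison or interaction test is named.

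Under "Participant characteristics collected" the plan lists autonomy versus paternalism, sanctity versus quality of life, health literacy, numeracy, religiosity (three DUREL subscales), number of children, NICU experience, race, ethnicity, education and year of birth. These enter one named analysis, a CART of treatment choice that also includes the experimental variables.

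The power analysis reads "Estimated 60% of participants choosing intensive care", "Detecting a 15% difference between study groups with at least 80% power and alpha of 0.05" and "Sample size of 1,050 necessary". The Background says of the earlier 30% versus 60% study that "they found the chance of survival did not affect their hypothetical perivable birth treatment choice".

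**The concern.** The experiment revisits a question on which an earlier study reported no effect, so a second null is a realistic outcome. A non-significant Fisher test cannot by itself tell a reader whether the effect is small or merely not shown. An interval can, and the plan does not ask for one.

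The Background also suggests that text-only presentation may have contributed to the earlier null. That amounts to asking whether format changes the response to the survival estimate, which is an interaction. None of the four tests estimates or directly tests that contrast, and it is where the sample gives least precision.

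Finally, covariates that might sharpen the randomised comparisons are collected but are not used for that purpose. CART yields splits and thresholds. It does not yield an adjusted effect of the randomised factors with an interval.

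**Working it through.** **Inputs from the plan.** 60% choosing intensive care; 15-point difference; 80% power; alpha 0.05; N = 1,050 over six equal cells. That gives 1,050/6 = 175 per cell, 525 versus 525 for survival, and 350 per format. Two-sided testing and the downward direction (60% to 45%) are inferred because they reproduce the stated N.

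**Assumption.** The proportion of variance in choice explained by covariates, R2, is not in the documents. The range 0.05 to 0.20 is used.

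**1. The plan's own figure.** For two proportions without continuity correction,

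n = [1.96 x sqrt(2 x 0.525 x 0.475) + 0.842 x sqrt(0.60 x 0.40 + 0.45 x 0.55)]^2 / 0.15^2 = 173 per cell.

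173 x 6 = 1,038, within 3% of 1,050. Power at 175 per cell is 80.5%. The sample size is therefore a cell-versus-cell calculation. By exact calculation, the planned Fisher test has 76.8% power for the same pair.

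**2. Main effects, unadjusted.** Power for 60% versus 45% is 99.8% for survival (525 versus 525) and 97.9% for a pair of formats (350 versus 350). The 95% half-width is 1.96 x sqrt(2 x 0.24/n):

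- n = 525: 5.9 points
- n = 350: 7.3 points
- n = 175: 10.3 points

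**3. Interaction, unadjusted.** Take the survival difference in one format minus that in another, from four cells of 175 with variance 0.24 each. SE = sqrt(4 x 0.24/175) = 0.0741, so the half-width is 1.96 x 0.0741 = 14.5 points. For a 15-point interaction, 0.15/0.0741 - 1.96 = 0.065, which gives 53% power.

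**4. Effect of adjustment.** The SE is multiplied by sqrt(1 - R2), equivalent to n/(1 - R2) per group. All power figures in the table use the normal approximation.

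| R2 (assumed) | SE factor | Effective n per cell | Power, 60% v 45%, one cell pair | Power, 15-point interaction | Half-width, survival (points) | Half-width, format pair (points) |
|---|---|---|---|---|---|---|
| 0 | 1.00 | 175 | 80.5% | 53% | 5.9 | 7.3 |
| 0.05 | 0.97 | 184 | 82.5% | 55% | 5.8 | 7.1 |
| 0.10 | 0.95 | 194 | 84.5% | 57% | 5.6 | 6.9 |
| 0.20 | 0.89 | 219 | 88.4% | 62% | 5.3 | 6.5 |

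A simulation of logistic standardisation (3,000 runs per setting, one normal covariate, no true effect) agrees. The SE ratio was 0.97-0.98 at R2 = 0.054 and 0.92 at R2 = 0.169, against sqrt(1 - R2) of 0.97 and 0.91.

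**5. Can 15 points serve as a margin?** Suppose 315/525 (60.0%) versus 268/525 (51.0%). The difference is 9.0 points, 95% CI 3.0 to 14.9, Fisher p = 0.004. The interval excludes 15, yet the effect is clearly present. A rule that equated exclusion of 15 points with no material effect would mislabel it.

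**The case against.** Unadjusted exact and rank tests are valid in a randomised experiment, and adjustment is a matter of efficiency. That stands: nothing here says that the planned tests would give wrong error rates.

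A reader might infer that the trial discards strong predictors of choice. The documents do not support this. They give no association between any characteristic and treatment choice, and at R2 = 0.05 the survival half-width moves only from 5.9 to 5.8 points.

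A reader might also infer that, without adjustment, the trial cannot bound a null result. That does not follow. Unadjusted intervals from the same counts, about 5.9 points either side for survival and 7.3 for a format pair, would do it. The omission lies in what is reported and is separate from the question of adjustment.

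Nor are the characteristics unused in multivariable work, since the CART includes them alongside the experimental variables. It simply answers a different question.

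The Aims name the two main effects and no interaction, and main-effect power is already high, so the power gains fall mostly on contrasts that the plan does not list. This is fair. The interaction still follows from the factorial design and the stated rationale.

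The timing objection also stands. The question order is not given, and the characteristics are listed after the outcomes. Answers on subjective numeracy, self-rated literacy, intrinsic religiosity and the two attitude items could be influenced by the randomised material if they were asked later.

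**Conclusion.** The concern holds as a gap in the plan that is free to close. The randomised comparisons of treatment choice have no effect estimate, interval or interaction contrast, and the CART does not supply an adjusted randomised effect.

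The size of the benefit from adjustment is conditional. Under an assumed R2 of 0.05 to 0.20, the SE falls by about 2.5% to 11%, cell-pair power rises from about 80% to 82-88%, and interaction power from 53% to 55-62%. For the main effects the gain is narrower intervals, with the survival half-width going from 5.9 to 5.3-5.8 points. If only the fixed characteristics can be used, the gain could be smaller. Reporting intervals and the interaction is worthwhile whatever R2 proves to be.

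**What to change.** - Analyse treatment choice by logistic regression on survival level, format and their interaction. Adjust for prespecified characteristics that the vignette cannot change: number of children, prior NICU exposure, race, ethnicity, education and year of birth.
- Add the DUREL scores, health literacy, numeracy, autonomy/paternalism and sanctity/quality-of-life items only if they were asked before the randomised material. State the question order in the plan.
- Report standardised risk differences with 95% confidence intervals for both main effects and the interaction.
- Keep the planned exact and rank tests, as sensitivity analyses wherever a model supplies the main estimate.
- Interpret a non-significant result by the range of differences that its interval excludes. Do not make exclusion of 15 points the criterion for no material effect: that figure is the plan's detectable difference and was not set as an equivalence margin.

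The cost is analysis wording and a little programming. No new data or participants are needed.
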